18.0 ETHICS/PROTECTION OF HUMAN PATIENTS

18.1 Institutional Review Board/Ethics Committee

Participating investigators must obtain IRB or EC approval prior to execution of the protocol. Only IRBs/ECs that comply with governmental requirements may approve this registry. Prospective investigators must provide to an IRB/EC this protocol, ICF and/or waiver, , and if applicable, any protocol amendments or other written information provided to the patients. This includes information to be completed by participants or the Investigator and staff, such as survey instruments or questionnaires, and any proposed advertising or recruitment materials. The approving IRB/EC will be responsible for the initial and continuing review and approval of this clinical registry. The participating investigators will be required to promptly report to the IRB/EC as required by the IRB/EC's policies. Additionally, investigators will be required to refrain from making any changes in the clinical registry plan without Sponsor and IRB/EC approval of an amended protocol, except where necessary to eliminate apparent immediate hazards to registry patients or others.

18.2 Applicable Regulations

This registry will be conducted in compliance with Good Clinical Practice and in accordance with the Declaration of Helsinki, as well as any other applicable local and country regulatory requirements.

18.3 Patient Information and Consent

Regulations concerning the protection of patients require that informed consent be obtained, or waiver approved by the IRB/EC where applicable, before a patient may participate in any clinical registry. For this registry, a patient must be consented or waiver approved by the IRB/EC before completing any registry specific procedures. Screening information that are part of SOC procedures may occur and be collected prior to consent, but the data may not be collected for registry purposes until the informed consent form (ICF) has been signed by the patient or waiver from the IRB/EC is received. A patient who signs the consent, or waiver is received, is considered enrolled.

An IRB/EC approved informed consent or waiver, where applicable, must be sought from each patient and must be appropriately documented in the patient's medical record. It is the Investigator's responsibility to obtain written informed consent from prospective patients or retrospective patients with prospective follow-up prior to registry-specific procedures. The Investigator may delegate this responsibility, if appropriately documented.

19.0 DATA HANDLING AND RECORD KEEPING

19.1 Data Elements

The following three categories of data will be captured in the registry database: (1) ablation procedure parameters, (2) patient parameters, and (3) healthcare provider parameters. The complete list of data parameters requested for this registry database are listed below.

1. Ablation procedure parameters:

- a) Procedure type: laparoscopic surgical; open surgical; percutaneous.
- b) Complete procedure duration from start of anesthesia administration (start time) to completion of the procedure (end time).
- c) Ablation duration for each individual ablation attempt (minutes and seconds).
- d) Ablation duration, defined as the time elapsed between first ablation probe puncture and removal of the last probe at the completion of the ablation.
- e) Type of anesthesia used during ablation procedure.
- f) Anatomical location of ablation.
- g) Liver stiffness near ablation site, if obtained prior by ultrasound or MRI.
- h) Smallest ablation margin, if available. Note: if less than 5mm margin, include reason (vessel, duct, location, bowel, other).
- i) Ablation Zone measurement, if available
- j) Use of hydrodissection during ablation procedure.
- k) Type of probe(s) (including serial number).
- l) Number of probes.
- m) Maximum probe temperature, per probe (°C).
- n) Power settings used per probe (Watts).
- o) Constant power vs ramp-up.
- p) Number of probe placement attempts per probe (to get the probe in position).
- q) Number of changes in probe placement throughout the ablation (after energy has been delivered).
- r) Location of probe placement relative to the target lesion (central, peripheral).
- s) Tract ablation (yes/no).
- t) If overlap of coagulation zones, provide overlap, if available.
- u) Needle navigation/placement guidance method used.
- v) Image fusion details, if applicable
- w) Identify if ablation procedure guidance software was used (i.e. for target identification, ablation monitoring, and/or ablation confirmation)
 - If NeuWave ablation confirmation software used, note use of the software, tissue contraction percentage, and the software version
 - If other software, note supplier/manufacturer
- x) If applicable, total number of CT and Xray scans used for the Ablation and total amount of radiation dose
- y) Imaging details (contrast, slice thickness if applicable).

2. Patient parameters:

- a) Patient lesion details at baseline:

- i. Type/origin of lesion: HCC, CRLM, CC, recurrent lesion (can be local recurrent or other intrahepatic recurrence), or metastatic lesion, if biopsy is performed.
- ii. Lesion size (measured in at least two dimensions), shape, and location (by liver segment).
- iii. Date of diagnosis of soft tissue liver lesion.
- iv. Lesion characteristics: stellate or smooth.
- v. Proximity to vasculature (specify name and distance to vasculature, if possible).
- vi. Proximity to other critical structures (specify, such as, bowel, stomach, skin, bile ducts, other).
- vii. Location of lesion: Superficial, exophytic, deep.
 - i. Exophytic: lesion extends beyond the contour of the liver
 - ii. Superficial: lesion that is within 10 mm of the capsule
 - iii. Deep: lesion that is deeper than 10 mm of the capsule
- viii. Modality used for lesion measurements (CT, MRI, PET, US, and/or X-ray)
- b) Patient medical, surgical, and radiation histories
 - i. Relevant medical history, in the opinion of the investigator
 - ii. Pre-treatment embolization or other chemotherapy.
 - iii. Relevant surgical history (any abdominal surgery or that is related to the soft-tissue lesion(s)).
 - iv. Radiation history.
 - v. Thermal ablation history.
 - vi. Biliary manipulation history.
 - vii. Other treatments for liver lesions.
- c) Family and genetic histories, as per SOC:
 - i. CRLM family history.
 - ii. HCC family history.
 - iii. Any other known genetic and molecular diagnostics available.
- d) Abuse and exposure histories, if available:
 - i. Alcohol history.
 - ii. Asbestos history.
 - iii. Hepatitis: B virus (HBV) / C virus (HCV), others and DNA level.
 - iv. Smoking history; tobacco, marijuana, other.

3. Healthcare provider parameters:

- a) Type of provider performing the ablation: abdominal imaging specialist, gastroenterologist, general surgeon, hepatologist, HPB surgeon, interventional radiologist, medical oncologist, surgical oncologist, ultrasonographer, other.

19.2 Source Documents

Source documents are documents on which information regarding patients is first recorded, including printed, optical, or electronic documents. Investigator patient files or hospital records, generally, are the basis of source document information. This includes, but is not limited to, original patient files; certified copies of patient records; hospital/clinic records; original recordings /tracing; digital images from automated instruments (e.g., cameras); radiographs; photographic negatives; and records kept at the site, at the laboratories and at other departments involved in the clinical registry.

Another type of source document is data from NeuWave Medical's Call Home Database. NEUWAVE Microwave Ablation System has a functionality that electronically collects procedure data and information during the ablation procedure and is transmitted by the NEUWAVE Microwave Ablation System to NeuWave Medical, after the conclusion of each ablation procedure; this information is collectively called the "Call Home Database." The procedure data includes, but not limited to, the following: date and time of procedure, anatomical location of ablations, number of ablations and power used for each ablation, type of probes used, and duration of procedure. Some of these relevant ablation procedure details will be provided to the site via a report generated from Call Home Database, if possible. The site will review the report and enter the procedure details into the registry's clinical database. Reports generated from the Call Home Database must be retained by the Investigator as part of the patient's permanent medical record. The report should be retained for review by the monitor. If a site is unable to receive the report generated from the Call Home Database, the relevant ablation procedure details should be manually recorded in the source documents from what is displayed on the NeuWave System monitor screen.

Source documents must be retained by the Investigator as part of the patient's permanent medical record. The information in the source documents is used to complete the eCRFs. All information captured on the eCRFs should be completely and accurately supported in source documentation. Any additional information relevant to the registry should be included in the source documents. In particular, any deviations from the registry protocol or procedures should be recorded in the source documents. The Investigator will retain originals of all source documents, patient consent form, and registry data.

19.3 Electronic Data Capture

An electronic data capture (EDC) system will be utilized by site personnel to transfer registry data from source records (medical records and/or source document worksheets) onto common eCRFs. This system is a web-based, secure electronic software application [REDACTED]. This system was designed, developed and maintained by [REDACTED] in a manner that is compliant with national and international GCP data protection/data privacy and electronic record/electronic signature (e.g., 21 CFR Part 11) regulatory requirements. The EDC system will be used to facilitate the collection of all registry data at the site. Designated site personnel will be responsible for entering patient data into the EDC system. All external and Sponsor internal users will be trained on the EDC application at a level dependent on their planned function. An EDC digital User Manual will be available under the help menu within the [REDACTED] website to assist in the collection and entry of source data into the electronic casebook.

[REDACTED] also has an image upload option called [REDACTED], which is where sites will be uploading all required scans.

A 24/7/365 Help Desk Support line (per [REDACTED] web site) staffed by the outsourced vendor will also be available to respond to site-monitor questions. Contact information for this help desk will be provided during site training.

19.4 Data Collection

Each EDC eCRF will be completed by the PI or PI's designee. Every effort should be made to respond to all monitoring and/or data management questions on each eCRF as completion of the data is required by the protocol. A unique ID number will identify each patient. The patient's unique ID number will be visible on each eCRF. At no time should the patient name appear on the eCRFs.

All data should be recorded accurately and completely. The Investigator is responsible for reviewing and approving each completed eCRF. Assurance of overall review and approval will be documented by the Investigator electronically signing each patient's electronic casebook.

19.5 Medical Dictionary Coding

Medical dictionary coding of medical history, concomitant medications, and verbatim AEs captured on eCRFs will be performed using a coding thesaurus algorithm. The Medical Dictionary for Regulatory Activities (MedDRA) and WHODrug dictionaries will be used after data entry and query resolution, via auto-encoding and interactive coding processes.

19.6 Data Correction

Required data corrections to eCRFs will be prompted via automated electronic edit checks and/or queries manually created by Sponsor reviewers. The change(s), individual making the change(s), and time the change(s) were made to the eCRFs will be automatically captured in the audit trail within [REDACTED].

19.7 Data Privacy

The collection, use, and disclosure of all personal data, including patient health and medical information, are to be maintained in compliance with applicable personal data protection and security laws and regulations that govern protected health information and the informed consent given by each registry patient. When collecting and processing such personal data, appropriate measures are to be taken to maintain the confidentiality of patient health and medical information and to prevent access by unauthorized persons.

20.0 REGISTRY SUSPENSION OR TERMINATION

The Sponsor may suspend or terminate the registry or one or more sites at any time. When this occurs, all patients at the site will be withdrawn and documented as early termination. Reasons for site or registry termination may include, but are not limited, to the following:

- Administrative concerns (e.g., inadequate patient enrollment, investigator/institution non-compliance, change of business strategy, etc.).
- Regulatory body mandates.

The Investigator also has the right to terminate participation in the registry at any time (e.g., for safety or inability to enroll patients). Should termination of a site be necessary, the Sponsor will provide procedures for termination.

21.0 DATA AND PUBLICATION POLICIES

[figure not shown]
Publication of the results of this registry will be governed by Johnson & Johnson publication policies, including current and applicable Medical Device Publication Policy. Any presentation, abstract, or manuscript will be made available for review by the Sponsor prior to submission. Licensing agreements or copyrights applying to tools, work products or intellectual property used during the registry should be observed and clearly displayed on registry documentation and publications, wherever appropriate.

All manuscripts of data obtained from this clinical registry will be reviewed and approved by the Sponsor and each author prior to any submission. All authors must disclose financial or personal affiliations that could be considered a conflict of interest.

22.0 SUPPLEMENTS

22.1 Numeric Pain Rating Scale

The Numeric Pain Rating Scale (NPRS) can be administered verbally (therefore also by telephone) or graphically for self-completion. As mentioned above, the respondent is asked to indicate the numeric value on the segmented scale that best describes their pain intensity.

22.2 Glossary

Acronyms/ Abbreviations	Terms
2D	2-Dimensional
AE	Adverse Event
APTT	Activated Partial Thromboplastin Time
ASA	American Society of Anesthesiologists
BMI	Body Mass Index
CBC	Complete Blood Count
CC	Cholangiocarcinoma
CFR	Code of Federal Regulations
CRLM	Colorectal Liver Metastases
CT	Computed Tomography
DSMB	Data Safety Monitoring Board
EC	Ethics Committee
ECOG	Eastern Cooperative Oncology Group
eCRF	Electronic Case Report Form
EDC	Electronic Data Capture
EORTC	European Organization for Research and Treatment of Cancer
EOS	End of Study
FeNo	Fractional Exhaled Nitric Oxide
GCP	Good Clinical Practices
GGT	Gamma-Glutamyl Transpeptidase
HCC	Hepatocellular Carcinoma
ICF	Informed Consent Form
IFU	Instructions for Use
INR	International Normalized Ratio
IRB	Institutional Review Board
LOS	Length of Hospital Stay
MRC SI	Member of the Royal College of Surgeons (Ireland)
NPRS	Numeric Pain Rating Scale

Acronyms/ Abbreviations	Terms
NSAIDs	Non-Steroidal Anti-Inflammatory Drugs
PAP	Positive Airway Pressure
PDM	Power Distribution Module
PET	Positron Emission Tomography
PI	Principal Investigator
PT	Partial Prothrombin
PTT	Partial Prothrombin Time
QOL	Quality of Life
SAE	Serious Adverse Event
SOC	Standard-of-Care
USV	Unscheduled (visit)

23.0 DOCUMENT FILING

A copy of all approved versions of the Registry Protocol will be kept by the site, in the Investigator Site File and in the Sponsor Trial Master File.

1.1 Study objective

1.1.1 Primary Objective

The primary objective of this registry is to compile data that will be analyzed at various timepoints, to understand the impact of selected parameters on procedure and patient outcomes. The database will capture data related to (1) Ablation Procedure parameters, (2) Patient parameters, and (3) Healthcare Provider parameters.

1.2 Study Design

This is a multicenter, observational registry that follows patients for a total of up to 5 years from the date of the first liver ablation procedure with either the NEUWAVE Microwave Ablation System or the NEUWAVE Microwave Ablation System with Ablation Confirmation.

This is an “umbrella registry,” which was included as an optional component in other NEUWAVE studies; hence, data from consenting patients who are or will be enrolled in other NEUWAVE soft tissue liver lesion ablation studies will be included in this registry. All other patients will be enrolled and followed prospectively, enrolled retrospectively with prospective, longitudinal follow up, or enrolled retrospectively with all retrospective follow up.

2 Treatment Assignment

This is a single-arm registry where all enrolled patients will be ablated using the NEUWAVE Microwave Ablation System as part of the site’s SOC treatment or per protocol for those patients who are also enrolled in other NEUWAVE studies.

3 Randomization and Blinding Procedures

As this is a single-arm registry, no randomization will occur, and no blinding procedures are required.

4 Interval Windows

Interval windows are provided in the Schedule of Assessments section of the study protocol. No additional windows are planned for analysis purposes.

5 Levels of Significance

No levels of significance are specified as no specific hypotheses about any of the outcomes of interest are being formulated or tested. Two-sided 95% confidence intervals (CI) will be estimated for specific endpoints for descriptive purposes only.

6 Analysis Sets

All Enrolled Set (AES): Consists of subjects who signed informed consent form or retrospectively enrolled with a waiver for signing informed consent form. The AES will be used for disposition of study subjects.

Full Analysis Set (FAS): FAS Consists of subjects who met inclusion/exclusion criteria and to whom the NeuWave Ablation device was utilized during procedure. Primary and secondary endpoints will be analyzed using FAS.

Safety Analysis Set (SAF): SAF Consists of subjects who met inclusion/exclusion criteria and to whom the NeuWave Ablation device was utilized during procedure. Safety endpoints will be analyzed using SAF.

7 Sample Size Justification

This registry will be open to receiving data from all patients who are ablated with microwave ablation of soft tissue liver lesions using the NEUWAVE Microwave Ablation System. Given that the objective of the registry is to investigate the relationships that exist between the stated clinical outcomes, patient and provider parameters, and microwave ablation (MWA) time and power, no power analysis or sample size determination have been performed given the absence of a specific hypothesis to test.

8 Statistical Analysis Methods

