7.0 REGISTRY DESIGN

7.1 Overall Registry Design and Plan – Description

This is a multicenter, observational registry that follows patients for a total of 5 years from the date of the first liver ablation procedure with the NEUWAVE Microwave Ablation System. The data gathered from participating sites will be available to be analyzed to develop ablation parameter guidance for ablation approaches under varying patient liver tissue conditions and liver lesions.

This is an “umbrella registry,” which was included as an optional component in other NEUWAVE studies; hence, data from consenting patients who are or will be enrolled in other NEUWAVE soft tissue liver lesion ablation studies will be included in this registry. All other patients will be enrolled and followed prospectively, enrolled retrospectively with prospective, longitudinal follow up, or enrolled retrospectively with all retrospective follow up.

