7.4 Exclusion Criteria

1. Patients with a life expectancy of less than 1 year, in the opinion of the treating physician.
2. Use of microwave ablation purely as a transection tool, rather than focused liver lesion ablation.

3. Patient is currently participating, or planning to participate, in another NeuWave/Ethicon-funded clinical trial or registry studying microwave ablation in the liver. Note: roll-over patients from previous NeuWave trials are permitted.

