7.6 Screen Failures

All patients signing consent who do not meet the eligibility or who do not have the ablation procedure initiated will be recorded as screen failures. The relevant eCRF pages (i.e. demographics and reason for screen failure) will be completed for all screen failure patients and thereby included in the registry database.

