17.7 Analysis Sets

All patients contributing data to the registry will be considered eligible for inclusion into planned analyses. Specific rules regarding a minimum or critical number of observed dependent and independent variables for inclusion into statistical modeling analyses will be specified in the SAP.

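### The SAP makes its safety set conditional on eligibility, exactly like its full analysis set, so a treated patient found ineligible is missing from every safety and efficacy rate

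*SAP*

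**What the plan says.** SAP section 6 names three sets.

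- The All Enrolled Set takes everyone with consent or a waiver. Its only stated use is disposition.
- For the full analysis set: "FAS Consists of subjects who met inclusion/exclusion criteria and to whom the NeuWave Ablation device was utilized during procedure". Its use: "Primary and secondary endpoints will be analyzed using FAS".
- For the safety set: "SAF Consists of subjects who met inclusion/exclusion criteria and to whom the NeuWave Ablation device was utilized during procedure". Its use: "Safety endpoints will be analyzed using SAF".

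SAP 8.7 plans no sensitivity analysis. SAP 8.13 provides for a listing of all reported adverse events.

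The protocol is broader. Section 17.7 states: "All patients contributing data to the registry will be considered eligible for inclusion into planned analyses". Sections 13.0 and 13.2 collect adverse events from first probe insertion and attach no eligibility condition. Section 7.6 counts among screen failures "All patients signing consent who do not meet the eligibility", and gives demographics and the reason for failure as the pages to complete.

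On other NeuWave studies the protocol says two things. Exclusion 3 in section 7.4 applies where "Patient is currently participating, or planning to participate, in another NeuWave/Ethicon-funded clinical trial or registry studying microwave ablation in the liver", with a note permitting roll-overs from previous trials. Section 7.1 says that "data from consenting patients who are or will be enrolled in other NEUWAVE soft tissue liver lesion ablation studies will be included". Protocol 17.2 and 17.3 and SAP sections 1.2 and 2 agree with 7.1.

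**The concern.** A safety set normally holds everyone exposed to the device, whether or not they should have been enrolled. Here it is filtered by eligibility. If eligibility is related to outcome, or is judged once the outcome is known, the reported complication rates describe a selected group. The same filter applies to technical success, technique efficacy, recurrence and survival.

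The filter also raises the stakes of an eligibility contradiction. Because both sets require the criteria to be met, the conflict between exclusion 3 and the umbrella design decides who is analysed, as well as who is enrolled.

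**Working it through.** The plan gives no figure on this point to reproduce: no ineligible fraction, no event rate and no power calculation (SAP section 7). The check is therefore mainly a reading of the passages against each other.

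**1. The two sets.** Both require eligibility and device use, so the safety set equals the full analysis set.

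**2. A treated patient who fails one criterion.** This patient is in the All Enrolled Set only. The patient is absent from all primary and secondary endpoint summaries, from the subgroup analyses of the primary endpoints (SAP 8.8) and from the adverse event summaries (SAP 8.13). SAP 8.10 names no set for the exploratory regressions, but their outcomes are primary endpoints, which section 6 assigns to the full analysis set. With no sensitivity analysis planned, no all-treated summary exists.

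**3. Against the protocol.** Section 17.7 has no eligibility condition. What it leaves to the SAP is rules on how many variables must be observed for modelling. The SAP gives no reason for the narrower sets.

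**4. How a treated patient can be ineligible.**
- *Prospective patients:* eligibility is checked at screening and confirmed before ablation (Protocol 12.1, 12.2), so late failures should be few.
- *Retrospective patients:* Protocol 9.3 allows enrolment after the ablation, even after all visits have taken place. Inclusion 1 (ablation per the Instructions for Use) then describes a procedure already performed. Exclusion 1 (life expectancy under 1 year, in the physician's opinion) may be judged when survival is already known.

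**5. Other-study patients.** Exclusion 3 read literally removes concurrent and planned participants from both sets. Roll-overs from previous trials remain in both.

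**6. Illustration of size.** Only N comes from the documents: 1,500, given as a maximum in the Protocol Summary and as a minimum in Protocol 7.2. Assumed: event rate r = 5% in eligible patients, ineligible share s, and risk ratio k in ineligible patients.

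- All-treated rate = (1 − s)·r + s·k·r
- Share of events missing from summaries = s·k / [(1 − s) + s·k], which does not depend on r

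| s | Patients left out | All-treated rate, k = 1 to 3 | Share of events missing, k = 1 to 3 |
|---|---|---|---|
| 2% | 30 | 5.0% to 5.2% | 2% to 6% |
| 5% | 75 | 5.0% to 5.5% | 5% to 14% |
| 10% | 150 | 5.0% to 6.0% | 10% to 25% |
| 20% | 300 | 5.0% to 7.0% | 20% to 43% |

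Example, s = 5% and k = 3: 1,425 × 0.05 = 71.25 events in the set and 75 × 0.15 = 11.25 outside it. The all-treated rate is 82.5/1,500 = 5.5%, and 11.25/82.5 = 14% of events are missing.

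At s = 10% and k = 3, the safety set would show 5.0% (95% Clopper-Pearson interval 3.9% to 6.3%, with 67.5 events rounded to 68 of 1,350). All treated patients would show 6.0% (4.9% to 7.3%, 90 of 1,500).

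**The case against.** The strongest case on the other side is that this is a single-arm, descriptive registry with broad criteria. Few treated patients should prove ineligible, and the illustrated shift in rate is mostly smaller than the sampling uncertainty. Protocol 17.7 is also permissive: it says who may be included, not who must be. Much of this stands as a limit on size. It does not explain why the safety set should be restricted at all.

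Several stronger readings are tempting, and the documents do not support them.

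- *The adverse events of ineligible patients vanish from the report.* They do not, because SAP 8.13 lists every reported event. What is lost is the rate, the denominator and the interval.
- *Anyone harmed in a procedure that departed from the Instructions for Use leaves the safety tables.* For a prospective patient confirmed eligible beforehand, a departure during the procedure does not clearly undo eligibility. Protocol 14.0 treats noncompliance as a deviation, and Protocol 13.1 counts use error among the criteria for a causal relationship. The reading fits mainly retrospective patients.
- *Protocol 7.6 means these events are never recorded.* Protocol 13.2 still requires entry from first probe placement, and 7.7 requires follow-up when an adverse event occurs at puncture without ablation. Section 7.6 is silent on ineligibility found after ablation and speaks only of patients who signed consent. That is a gap in clarity, not an instruction to omit events.
- *The whole umbrella cohort is lost.* Roll-overs are expressly permitted. The contradiction over concurrent patients lies within the protocol itself; the SAP's eligibility condition carries it into the analysis.
- *Ineligible patients are the ones most likely to have complications.* Nothing in either document says so. With k = 1 the reported rate is unchanged, and with k below 1 the safety set would overstate risk.

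**Conclusion.** The point holds for summary rates and denominators. As written, the SAP has no analysis of all treated patients, for safety or efficacy. This departs from Protocol 17.7 and does not match the protocol's own start of adverse event collection. Selection related to outcome is a real possibility for retrospective patients and much less of one for prospective patients. Concurrent co-enrollees would drop out if exclusion 3 is applied literally.

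The size is unknown. The table in the working rests on assumed values of s, k and r and shows only the range: little movement in the rate when few patients are ineligible, but a loss of events from the summaries even when their risk is no higher. That loss matters most for rare serious complications, where one or two events change the estimate. The case for correction rests on the definition and the contradictions, not on any of the illustrated figures.

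**What to change.** - **Safety set (SAP 6):** all patients in whom the NeuWave device was used, counted from first probe insertion, regardless of eligibility.
- **Full analysis set (SAP 6):** align it with Protocol 17.7. Alternatively, keep the eligible-only set, give the reason, and add an all-treated supportive analysis, amending SAP 8.7 to match.
- **Adverse event incidence (SAP 8.4.2, item 6, and 8.6):** assign it explicitly to the safety set. It is also a secondary endpoint, so section 6 at present sends it to the full analysis set, and the two denominators would differ once the safety set changes.
- **Protocol 7.6:** state that a patient found ineligible after probe insertion is not handled as a screen failure for adverse event collection and analysis, and cover waiver patients.
- **Exclusion 3 against Protocol 7.1, 17.2 and 17.3 and SAP 1.2 and 2:** reconcile these passages, so that it is clear whether concurrent participants in other NeuWave liver studies are in or out.

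The cost is SAP wording, a short protocol clarification and, if the eligible-only set is kept, one more set of tables. No new patients or procedures are needed. The downside is slight added heterogeneity from a few ineligible patients. The changes should be settled before database lock.
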